1. Test the hypothesis that patients with right hemisphere stroke and frontotemporal dementia (FTD) show more improvement on untrained tests of social cognition after web-based social-cognitive training exercises (Posit Science Inc.) than after non-specific cognitive training.
2. Evaluate patients with FTD and stroke in multiple domains of social cognition (such as emotional contagion, affective perspective-taking, and affective prosody identification) as well as mood, attention, and working memory, before and after intervention to identify which functions improve after training.
3. Assess the feasibility and acceptability of web-based interventions in patients with stroke or FTD through examination of usage data and patient feedback.
4. Determine the effects of location of lesion or focal atrophy on improvements in social-cognitive training exercises with intervention.

3. Background (briefly describe pre-clinical and clinical data, current experience with procedures, drug or device, and any other relevant information to justify the research)

Problem: Both patients with stroke or FTD can experience impairments in social-emotional functioning. While the profile of deficits may differ in these two illnesses, there are convergent issues in empathic abilities especially in right hemisphere stroke and behavioral variant FTD. Deficits or deterioration in empathy can impact patients' interpersonal relationships and adversely impact patients' quality of life. However, there are currently very few treatments that specifically target these issues, and many of them are limited in their scope and effectiveness. Recently, web-based training interventions have shown efficacy in treating functional impairments in stroke and social deficits in other disorders such as schizophrenia. It is crucial to test whether this cost-effective and mobile intervention can be effectively utilized to treat social-emotional deficits in patients with stroke or FTD.

4. Study Procedures

- a. Study design, including the sequence and timing of study procedures (distinguish research procedures from those that are part of routine care).

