Based on medical chart review, all patients will first be screened for eligibility. Patients will only be enrolled in the study if they meet both inclusion and exclusion criteria. The study will be explained to the patient and informed consent will be obtained before they undergo baseline social and cognitive assessments and receive a laptop to begin either a social-cognitive or control training condition (randomly determined by selecting one of 30 sealed envelopes).

Following the completion of the 20-30 hours of training over the course of 4 weeks, the patient will be assessed with the same measurements again. The patient will then complete the second training condition (20-30 hours over 4 weeks) that they were not randomly assigned to initially. The patient will then receive a final assessment, return the laptop, and receive compensation for the study.

Each of the three assessments will include the following tests: 1) Star Cancellation test, an assessment of spatial attention (Friedman, 1992); 2) Interpersonal Reactivity Index (IRI), a subjective evaluation of 4 components of empathy, rated by the caregiver (Davis, 1983); 3) Reading the Mind in the Eyes Test (RMET), an objective evaluation of empathy (Baron-Cohen

et al., 2001); 4) Social Cognitive Tasks from the University of Pennsylvania Computerized Neurocognitive Battery (Penn CNB), a measure of affect perception and facial memory (Gur et al., 2010); 5) Prosody Battery, a well-validated test of expression and production of prosody (Ross and Monnot, 2008; Ross et al., 1997); 6) Forward and Backward Digit Span, a brief assessment of attention and working memory; 7) Faux Pas Test, a test of social awareness (Gregory et al., 2002); and 8) the Patient Health Questionnaire-9, a well-validated screening tool for depression (Kroenke et al., 2001). The IRI must be completed by a caregiver or spouse.

b. Study duration and number of study visits required of research participants.

The study duration is around 8 weeks for each participant and will require 3 total participant visits for the baseline, 1st post-treatment (1st condition), and 2nd post-treatment (2nd condition) assessments. If there are technical issues with the laptop or online portal, assistance will be provided remotely if possible.

c. Blinding, including justification for blinding or not blinding the trial, if applicable.

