- c. Justification and safety information if non-FDA approved drugs without an IND will be administered. N/A

7. Study Statistics

- a. Primary outcome variable.

Change in performance from baseline to 1st post treatment on Penn CNB tasks (Total) vs. 1st post-treatment (new baseline) to 2nd post-treatment on Penn CNB tasks (total).

- b. Secondary outcome variables.

Changes in total and subtest scores on IRI, Prosody Battery, RMET, Faux Pas Test, and star cancellation.

- c. Statistical plan including sample size justification and interim data analysis.

We will compare the change in means of outcome measures after social cognition treatment vs. control treatment. The primary outcome variable will be change in performance on the Penn CNB tasks after the end of each treatment. The null hypothesis is $H_0: \mu_1 = \mu_2$, where μ_1 is the mean change in performance on the Penn CNB tasks between pre-treatment and post-treatment with social cognition treatment and μ_2 is the mean performance on the Penn CNB tasks between pre-treatment and post-treatment with control treatment.

Analyses. In a cross-over trial, it is essential to evaluate the effect of condition versus the effect of sequence of the treatment, and to evaluate for carry-over from one treatment to the next. Based on our clinical experience we expect little change in the Penn CNB with the control (non-specific cognitive exercises) in chronic right hemisphere stroke (as we see decline rather than recovery in chronic stroke in these functions), and little change or decline in patients with behavioral variant FTD. But we will evaluate the effect of condition versus sequence independently. The primary analyses will evaluate the change in performance on Penn CNB as the dependent variable, $Y_{ij} = \mu + S_i + \mu_{(j)} + C_{(j)} + e_{ij}$ where i represents a subjects, j represents the sequence (1 or 2). The Y_{ij} is the change in the evaluations. The S_i represents the random effect of the subjects. The $\mu_{(j)}$ represents the means of the two treatments (social cognition or control). The $C_{(j)}$ represents the carryover effects. The test for the treatment effect can be obtained from this model. Firstly, the effect of carryover effects will be tested at $p < 0.1$. If this is significant, then only the first sequence data will be analyzed as this sequence is free of carryover effects. A similar analysis will be done for the change in accuracy of secondary outcome variables.

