Power. We expect to enroll up to 50 patients in the study, and expect 20-30 participants will complete the study. Because of the social cognitive deficits in these patients (accompanied by relatively low insight and motivation), there is likely to be high attrition. If the sample size in each treatment group is 13, (a total sample size of 26) a crossover design will have 86% power to detect a difference in means of 6 (the difference between treatment mean change in accuracy, μ_1 , of 10 and a control mean change in accuracy, μ_2 , of 4) using a two group t -test with a two-sided alpha of 0.05.

- d. Early stopping rules.

Patients will be allowed to stop at any time, but they will not receive compensation if they fail to complete all criteria for compensation. Their data will only be used for Aim 1 if they complete the entire study. We may be able to use data from participants who complete the social-cognition treatment condition only for Aims 2 and 3.

8. Risks

- a. Medical risks, listing all procedures, their major and minor risks and expected frequency. There are no known risks associated with the training software, use of a laptop computer, or the assessments used in this study. Participants could become bored, anxious, or embarrassed during assessment of cognitive function.
- b. Steps taken to minimize the risks. The participant will be able to stop participation at any time if they experience any issues with the use of the training software or assessments of social abilities.
- c. Plan for reporting unanticipated problems or study deviations. The PI will report unanticipated problems or study deviations to the IRB immediately.

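### Section 7d lets leavers who finished social training into Aim 2, has no matching rule for leavers who finished control training, and the 7c model writes no period term to absorb the imbalance

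*Combined protocol and SAP*

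**What the plan says.** Section 7d (Early stopping rules) sets two rules for people who leave early. For Aim 1: "Their data will only be used for Aim 1 if they complete the entire study". For the other aims, the investigators may be able to use "data from participants who complete the social-cognition treatment condition only for Aims 2 and 3". No section makes a similar provision for someone who finished only the control condition.

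Section 4a gives the order of events: baseline tests, first condition, the same tests again. Then "The patient will then complete the second training condition", followed by a final assessment. All three visits use the same eight tests.

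Objective 2 in section 2 covers several domains of social cognition and also working memory, attention and mood. They are measured "before and after intervention to identify which functions improve after training". The objective names no comparator.

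Section 7c gives a model for change scores with a random subject effect, a treatment effect and a carryover effect. For the rest it says: "A similar analysis will be done for the change in accuracy of secondary outcome variables". Section 7b lists the IRI, Prosody Battery, RMET, Faux Pas Test and star cancellation. Digit Span and PHQ-9 are among the tests in 4a but appear in neither 7a nor 7b. Section 4e expects that the control exercises may help general attention, though not social cognition.

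**The concern.** Take two patients who both stop after the 1st post-treatment visit. One had social training first, the other control training first. They have had the same tests at the same two visits. Section 7d offers a place in Aim 2 to the first patient only, so what decides is the condition received, not the data available.

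This matters in two ways. In a comparison of conditions, the extra patients add data to one side and from one period, so anything that differs between a first and a second retest (practice, decline) can leak into the social-minus-control contrast. In a before-after reading of social training, nothing separates a training effect from change that would have occurred anyway. Objective 2 is meant to say which functions improve, so either route could put a function on that list, or keep it off, for the wrong reason.

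**Working it through.** **Plan's own figure.** The plan gives no figure for this point. Its 86% power (13 per group, difference 6, two-sided 5%) cannot be reproduced forward because no SD is stated. Solving backwards gives an SD of 4.83 for a two-group t-test, or 9.65 to 9.67 for the within-patient difference with 26 patients. The bias below does not depend on the SD.

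**Who the added patients are.** A control-first patient reaches social training only in the second period. If that patient then has the post-social assessment, nothing is left to leave early from. So a leaver with post-social data is always social-first, and each contributes one first-period social change. This holds whether the word *only* in the 7d sentence is attached to the condition or to the aims.

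**How many.** Section 7c says "We expect to enroll up to 50 patients in the study", and the investigators "expect 20-30 participants will complete the study". If 50 enrol, 20 to 30 leave. With the 26 completers of the power statement, 50 − 26 = 24 leave. An even split by order gives 12 social-first leavers, and 12 is reached only if all of them stay until the 1st post-treatment visit. The documents do not say when people leave, so I use k = 3, 6 and 12 as assumptions.

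**Formula.** Take 13 completers per order plus k social-first leavers. Let d be the first-period minus second-period difference in mean change, and ρ the correlation between a patient's two changes. In a random-subject model with a treatment term and no period term (carryover term dropped):

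- first-period share of social changes = (13 + k)/(26 + k); for control changes it is 13/26 = 0.5
- bias in social minus control = (1 − ρ) × d × [(13 + k)/(26 + k) − 0.5]

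With ρ = 0 this is the simple difference in means. A direct generalised least squares calculation gives the same values for k = 6 and k = 12.

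**Results for an assumed d = 4 points.**

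| k | share of social changes from period 1 | bias, ρ = 0 | ρ = 0.3 | ρ = 0.5 |
|---|---|---|---|---|
| 3 | 16/29 = 0.552 | 0.21 | 0.14 | 0.10 |
| 6 | 19/32 = 0.594 | 0.38 | 0.26 | 0.19 |
| 12 | 25/38 = 0.658 | 0.63 | 0.44 | 0.32 |

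The bias is proportional to d: halved at d = 2, zero at d = 0, and against social training if d is negative. The two changes share the middle assessment with opposite signs, which pulls ρ down, so the ρ = 0 column should not be dismissed.

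**Does equal treatment of leavers suffice?** Only if their numbers match. With 12 social-first and 6 control-first leavers the shares are 25/38 = 0.658 and 19/32 = 0.594, and the simple bias is 4 × 0.064 = 0.26. With the numbers reversed it is −0.26. Adding a period term brings the period bias to 0 in the model calculation.

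**If the 7c carryover test is significant.** Only first-period data are then used, so the period imbalance disappears. The social side would still hold completers plus leavers, and the control side completers alone.

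**Before-after reading.** For the outcomes listed in 7b, section 7c states a controlled analysis. For Digit Span and PHQ-9 no analysis is stated, so an uncontrolled reading is open there. Section 4e's remark on general attention bears directly on Digit Span.

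**The case against.** The 7d sentence is permissive, and nothing bars control-condition leavers. Section 7c commits to comparing conditions and extends that to the secondary outcomes. It also promises to evaluate condition and sequence separately and uses *first sequence* to mean the first period, so order is not ignored. Section 4a mentions 30 sealed envelopes. If each is used once, 26 completers leave at most 4 leavers, and the bias at d = 4 is at most 4 × (17/30 − 0.5) = 0.27. Aim 1 is untouched, and the abstract presents the search for affected domains as a hope.

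Most of this stands and limits the point. It does not remove it. The intention to separate order from condition is not carried into the equation as a period term, 7c does not say how leavers enter, and two Aim 2 measures have no stated analysis.

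Three stronger readings are tempting and not supported:

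- *Control leavers are excluded by rule.* They are left out by omission.
- *The rule favours social training on every measure.* The sign follows the period difference, which the documents do not give. The IRI is rated by a caregiver, so patient practice is a weak mechanism there.
- *The plan expects 40% of a before-after gain to be non-specific* (4 under control against 10 under social training). Those are planning values for the primary outcome. Section 7c itself expects little change or decline on the Penn CNB under control, and the values do not carry over to other scales.

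**Conclusion.** The point holds as a gap in the Aim 2 rule. Used as written, 7d adds one-sided, first-period data to a comparison with no period term, or supports a before-after reading with no comparator, mainly for Digit Span and PHQ-9.

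The shift in the contrast is modest: about 0.10 to 0.63 points for an assumed 4-point period difference, 3 to 12 social-first leavers, 13 + 13 completers and ρ from 0.5 down to 0. Set against the 6-point difference of the power statement, that is about 2% to 11% (0.10/6 and 0.63/6). This is an illustration only, since the 6 belongs to the Penn CNB. Period difference, correlation and leaver numbers are assumptions, and the direction is unknown. The lack of a comparator in a before-after reading is the more serious of the two routes. The primary analysis is not affected.

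**What to change.** Replace the 7d sentence, as far as it concerns Aim 2, with:

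> For Aim 2, all available period changes are included for every participant assessed at the 1st post-treatment visit, whichever condition came first, and completers' second-period changes are kept. Improvement on every Aim 2 measure, including Digit Span and PHQ-9, is judged by the social-minus-control contrast from the section 7c mixed model with a period term added. A completers-only analysis is a sensitivity analysis.

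The period term is needed as well as the common rule, because the numbers of leavers will rarely match. The cost is a few lines of text and slightly more analysis. No new data are needed, since control-first leavers who reach that visit have already been tested. Some functions that look better before-after will no longer be called improved. The change does not remove bias from selective dropout, so the report should give the number of leavers by order and by time of leaving.

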Double-blinding is not possible in this study due to the large difference in the training content between the two training conditions.

d. Justification of why participants will not receive routine care or will have current therapy stopped.

Participants will receive their routine care, medications, or therapies while enrolling in this study. Cognitive rehabilitation for chronic right hemisphere stroke and behavioral variant FTD is very rare, so we anticipate most patients will be receiving no specific therapy for the deficits being targeted.

e. Justification for inclusion of a placebo or non-treatment group.

There is no placebo or non-treatment group in this study. There is a control condition (non-specific cognitive exercises) that we expect may improve general attention, but we do not expect such training to affect social cognition.

f. Definition of treatment failure or participant removal criteria.

N/A.

g. Description of what happens to participants receiving therapy when study ends or if a participant's participation in the study ends prematurely.

Participating in this current study is independent of their routine medical care. Therefore, if they prematurely end participation in the study or complete the study, patients will still continue their standard care.

5. Inclusion/Exclusion Criteria

Inclusion criteria:

1. Clinical diagnosis of right hemispheric stroke or behavioral variant frontotemporal dementia.
2. Able to give informed consent.
3. Premorbid proficiency in English (by self-report).
4. Age 18 or older.
5. Score of 21 or higher on the mini-mental state examination.

Exclusion criteria:

1. Prior history of neurological disease affecting the brain other than stroke or frontotemporal dementia (e.g., brain tumor, multiple sclerosis, traumatic brain injury)
2. Known uncorrected hearing loss
3. Known uncorrected vision loss
4. Prior history of severe psychiatric illness, developmental disorders, or mental retardation (e.g., schizophrenia, autism spectrum disorders).
5. Score of 20 or lower on the mini-mental state examination.

6. Drugs/ Substances/ Devices

- a. The rationale for choosing the drug and dose or for choosing the device to be used. N/A, no drugs to be used.
- b. Justification and safety information if FDA approved drugs will be administered for non-FDA approved indications or if doses or routes of administration or participant populations are changed. N/A

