- d. Legal risks such as the risks that would be associated with breach of confidentiality. Results of cognitive training and assessment measures will be kept strictly confidential and only the investigators participating in this study will have access to these records. If the patient wishes to know the results, or wishes to have them sent to one or more care providers, the results will be made available. If we identify any problems in thinking skills, the patient will be given the option of referral to rehabilitation specialists after the treatment study. If we identify depression (a score of 10 on the PHQ-9 or a score >0 on item 9, regarding suicidal thoughts, we will refer the patient for evaluation and treatment of depression if they are not already receiving treatment for depression. There is a small risk of breach of confidentiality, resulting in information about cognitive deficits or diagnosis being disclosed to individuals who are not care providers. There are no known legal risks, although such a breach in confidentiality might affect the person's employment. The only people who will know the patients are in a research study and will see the information about patients are members of the research team. Patients will be assigned codes for data collection and analysis. Data will be kept in locked file cabinets or secure computers that are password protected. When the study is over and the results are public, no information linked to the patient will be included. We will not collect sensitive information.
- e. Financial risks to the participants. All costs of study procedure and training modules will be provided to the patient for free at no cost to the patient or his/her insurance company.

9. Benefits

- a. Description of the probable benefits for the participant and for society.
- b. Individual participant. The study might improve a participant's cognitive and social-emotional functioning if the training is effective. The participant will also receive a small financial compensation if they complete the study (see below).
- c. Society. The results of this work may provide a novel treatment option in right hemisphere stroke and behavioral variant frontotemporal dementia and allow for future development of further interventions that target social-emotional deficits in right hemisphere stroke and behavioral variant frontotemporal dementia. Identifying a cost-effective treatment intervention will also contribute to the overall care of stroke patients.

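### Section 8d states no action when a patient already treated for depression reports suicidal thoughts on PHQ-9 item 9

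*Combined protocol and SAP*

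**What the plan says.** Section 4a lists "the Patient Health Questionnaire-9, a well-validated screening tool for depression" among the tests given at each of the three assessments (baseline and after each training condition).

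The only rule for acting on the result is in section 8d. Depression counts as identified if the PHQ-9 score is 10 (read here as 10 or higher) or if there is "a score >0 on item 9, regarding suicidal thoughts". The response is then: "we will refer the patient for evaluation and treatment of depression if they are not already receiving treatment for depression".

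The same section has two sentences on who sees results. If the patient asks to know them, or "wishes to have them sent to one or more care providers, the results will be made available". And the only people who will know that patients are in the study and "will see the information about patients are members of the research team".

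Section 4d lets participants keep their usual care, medication and therapy. Exclusion criterion 4 in section 5 covers a history of severe psychiatric illness, with schizophrenia and autism spectrum disorders as its examples, and does not name treated depression.

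**The concern.** The two triggers do different jobs. A total at the threshold says that the patient may be depressed. If the patient is already being treated, a referral for treatment adds little, and the exemption makes sense. A positive item 9 is a report of suicidal thoughts, and section 8d itself makes it a trigger in its own right, whatever the total. Being in treatment does not make that report redundant, because the treating clinician may not know what the patient answered at a study visit.

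One exemption covers both triggers. A team that follows 8d to the letter could therefore record suicidal thoughts in a treated patient and have no written step to take. What is at stake is the safety of that patient, not the estimate or the test.

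**Working it through.** The plan gives no figure to reproduce. The check is a reading of the rule, followed by a search of the text for anything that fills the gap.

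**The rule as written.** (Total at threshold OR item 9 above 0) AND not already treated for depression → refer. The four cases are:

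- Total at threshold, untreated: refer.
- Total at threshold, treated: no action stated. This is reasonable, since the referral would be redundant.
- Item 9 above 0, untreated: refer.
- Item 9 above 0, treated: no action stated. This is the gap.

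The bracket that opens before the triggers in 8d is never closed. It could be closed after the total-score trigger or after the item 9 trigger. The exemption still governs item 9 either way.

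**Can the fourth case occur?** Yes. The rule itself provides for treated patients, section 4d continues their therapy, and exclusion criterion 4 does not remove them as such. The PHQ-9 is given three times, so a patient who completes the study has three occasions on which it could arise.

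**Does any other section state a response?**

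- 4f (treatment failure or removal criteria): marked not applicable.
- 8b (minimising risk): the participant may stop.
- 8c (reporting): unanticipated problems and deviations go to the IRB, with no step for the individual patient.
- 8d (release of results): to care providers at the patient's wish, not at the study's initiative.

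None of these is a stated response to item 9.

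**How many patients?** The documents give no rate. For illustration only, assume that a share t = 0.10 to 0.40 of patients is treated for depression, and that a share s = 0.05 to 0.20 of those scores above 0 on item 9 at least once. Neither range comes from the documents. The product t × s then runs from 0.10 × 0.05 = 0.005 to 0.40 × 0.20 = 0.08.

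Section 7c says: "We expect to enroll up to 50 patients in the study, and expect 20-30 participants will complete the study". The PHQ-9 is given at baseline, so the exposed group is everyone assessed at baseline, not only completers. With n = 50 as the upper limit:

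- Expected number affected, n × t × s: 50 × 0.005 = 0.25 to 50 × 0.08 = 4.
- Chance of at least one, 1 − (1 − t × s)^n: 1 − 0.995^50 = 0.22 to 1 − 0.92^50 = 0.98.

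With n = 20, the lower completer figure, the expected number is 0.1 to 1.6 and the chance of at least one is 0.10 to 0.81. A range this wide carries little information. The point rests on the wording of the rule and not on these numbers.

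**The case against.** The strongest reply is that the affected patients are the ones who already have depression care, and that section 4d keeps it going. Severe psychiatric illness is excluded, the likely number is small, and the consent pages, where handling of suicidal thoughts could be described, are not in the file. The investigators may well act on a positive item 9 whatever 8d says. All of this stands, and it limits the weight of the point. It does not supply a written response, and the protocol text supplied refers to no separate procedure.

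Three stronger readings are tempting and should not be made.

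- A reader might infer that the protocol blocks every route to the treating clinician except a request from the patient. It does not. The sentence limiting information to the research team cannot be an absolute bar, because the referral rule in the same section already involves outside clinicians. Section 8d also describes a breach as disclosure to people who are not care providers. Other routes are unspecified, not closed.
- A reader might cite section 4g, "Participating in this current study is independent of their routine medical care", as evidence that clinicians are kept uninformed. That sentence answers what happens when participation ends, and goes on to say that standard care continues. It says nothing about sharing results.
- A reader might argue from section 7c, where the deficits are "accompanied by relatively low insight and motivation", that patients would not ask for their results to be sent. The phrase explains expected attrition. It is not a statement about reporting mood or requesting results, and inclusion requires the ability to consent and a mini-mental state score of 21 or higher.

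**Conclusion.** The point holds in a limited form. In the protocol text supplied, the exemption in 8d leaves a treated patient with item 9 above 0 without any specified action. The cause is a stated rule that, if followed, produces no response. It is not simply a missing operational detail.

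Its size cannot be estimated from the documents, and the number of patients is probably small. No sample size, power or significance figure is affected. The conclusion assumes that no consent text or site procedure outside the file already covers the case. It is best classed as a cheap improvement for patient safety: the case for it is the seriousness of a single unanswered report set against the low cost of the change.

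**What to change.** Rewrite the 8d rule in three parts.

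1. For patients not being treated for depression, keep the present rule unchanged: a total of 10 or higher, or item 9 above 0, leads to referral for evaluation and treatment of depression.
2. For patients already in treatment, keep the exemption for the total score only.
3. Add one sentence, for example: *If item 9 is above 0 in a patient already receiving treatment for depression, we will promptly notify the clinician treating the depression, seeking the patient's agreement first.*

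Part 1 matters. A general rule to notify the treating clinician for any positive item 9, with referral only where there is none, would weaken the present protection. An untreated patient with a total below 10 who is under a neurologist would then get a notification in place of today's referral.

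Add a matching line on confidentiality in 8d and in the consent form. It should say what happens if the patient does not agree, as an exception to the sentence that only the research team sees patient information.

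The cost is a few sentences and no new visit or instrument. Someone must read item 9 soon after each assessment. The documents do not say who runs the assessments, so the role has to be named. The downsides are a few extra notifications and a stated limit on confidentiality that some patients may dislike.
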